##### **Secondary:**

The secondary analysis involves a comparison of the secondary outcome measures between the two surgical treatment groups. The ASES, Constant Score, and imaging healing rates will be analyzed for differences between the two groups at 8 years. The planned secondary analyses are performed using a 5% significance level. No p-value adjustment is required for multiple outcomes, as treatment effectiveness is based only on the primary variable.

#### **4.12 What is the proposed frequency of analyses?**

The analysis will occur once all eligible patients have been recruited and all patient data has been collected.

#### **4.13 What is the estimated cost and duration of the trial?**

The duration of this trial will be 1 year. This study does not have any direct costs.

### **DETAILS OF TRIAL TEAM**

#### **Trial management:**

#### **What are the arrangements for day to day management of the trial?**

The orthopedic research study coordinator is responsible for the day to day management of the trial. This includes: general administrative details, collecting, monitoring, tracking and analyzing data. The Study Research Coordinator (SRC) has experience in biostatistics, computer technology, epidemiology and study management. He/she is available to answer questions on a daily basis. **Quality Monitoring:** Forms: All forms are checked by the SRC for completeness, consistency and extreme values. **Appointments:** The SRC is responsible for monitoring participant visits **Equipment:** The scales used to measure power are calibrated. **Data Management:** is supervised by the study biostatistician. Data is collected on standardized Case Recording Forms (CRF). Any revisions to the CRF's are dated to maintain an audit trail of these changes. CRF's are signed and dated by the clinical investigator.

**5. APPENDICES**

**Appendix A: Outcome Measures**

WESTERN ONTARIO

**ROTATOR CUFF INDEX**

**(WORC)©**

**A disease-specific quality of life measurement tool for patients  
with rotator cuff disease**

Patient Initials: \_\_\_\_\_

[figure not shown]

## INSTRUCTIONS TO PATIENTS

In the following questionnaire you will be asked to answer questions in the following format and you should give your answer by putting a slash "/" on the horizontal line.

[figure not shown]
### NOTE:

1. If you put a slash "/" at the left end of the line i.e.

then you are indicating that you have no pain.

2. If you put your slash "/" at the right end of the line i.e.

then you are indicating that your pain is extreme.

3. Please note:

- a) that the further to the right you put your slash "/", the **more** you experience that symptom.
- b) that the further to the left you put your slash "/" , the **less** you experience that symptom.
- c) **please do not place your slash "/" outside the end markers**

You are asked to indicate on this questionnaire, the amount of a symptom you have experienced in the past week as related to your problematic shoulder. If you are unsure about the shoulder that is involved or you have any other questions, please ask before filling out the questionnaire.

If for some reason you do not understand a question, please refer to the explanations that can be found at the end of the questionnaire. You can then place your slash "/" on the horizontal line at the appropriate place. **If an item does not pertain to you or you have not experienced it in the past week, please make your "best guess" as to which response would be the most accurate.**

**WORC**  
**Section A: Physical Symptoms**  
**INSTRUCTIONS TO PATIENTS**

**The following questions concern the physical symptoms you have experienced due to your shoulder problem. In all cases, please enter the amount of the symptom you have experienced in the last week. (Please mark your answers with a slash "/")**

[figure not shown]
1. How much sharp pain do you experience in your shoulder?

2. How much constant, nagging pain do you experience in your shoulder?

3. How much weakness do you experience in your shoulder?

4. How much stiffness or lack of range of motion do you experience in your shoulder?

5. How much are you bothered by clicking, grinding or crunching in your shoulder?

6. How much discomfort do you experience in the muscles of your neck because of your shoulder?

[figure not shown]
**WORC**  
**SECTION B: Sports/Recreation**  
**INSTRUCTIONS TO PATIENTS**

**The following section concerns how your shoulder problem has affected your sports or recreational activities in the past week. For each question, please mark your answers with a slash "/". )**

7. How much has your shoulder affected your fitness level?

8. How much difficulty do you experience doing push-ups or other strenuous shoulder exercises because of your shoulder?

9. How much has your shoulder affected your ability to throw hard or far?

[figure not shown]
10. How much difficulty do you have with someone or something coming in contact with your affected shoulder?

**WORC**  
**SECTION C: Work**  
**INSTRUCTIONS TO PATIENTS**

**The following section concerns the amount that your shoulder problem has affected your work around or outside of the home. Please indicate the appropriate amount for the past week with a slash "/".**

11. How much difficulty do you experience in daily activities about the house or yard?

[figure not shown]
12. How much difficulty do you experience working above your shoulder?

13. How much do you use your unininvolved arm to compensate for your injured one?

14. How much difficulty do you experience lifting heavy objects at or below shoulder level?

[figure not shown]
difficulty

difficulty

[figure not shown]
**WORC**  
**SECTION D: Lifestyle**  
**INSTRUCTIONS TO PATIENTS**

**The following section concerns the amount that your shoulder problem has affected or changed your lifestyle. Again, please indicate the appropriate amount for the past week with a slash "/".**

[figure not shown]
15. How much difficulty do you have sleeping because of your shoulder?

16. How much difficulty have you experienced with styling your hair because of your shoulder?

[figure not shown]
17. How much difficulty do you have "roughhousing or horsing around" with family or friends?

18.

How much difficulty do you have dressing or undressing?

**WORC**  
**SECTION E: Emotions**  
**INSTRUCTIONS TO PATIENTS**

**The following questions relate to how you have felt in the past week with regard to your shoulder problem. Please indicate your answer with a slash "/".**

[figure not shown]
19. How much frustration do you feel because of your shoulder?

20. How "down in the dumps" or depressed do you feel because of your shoulder?

21. How worried or concerned are you about the effect of your shoulder on your occupation?

---

---

---

## THANK YOU FOR COMPLETING THE QUESTIONNAIRE

### American Shoulder and Elbow Surgeons Standardized Shoulder Assessment Form (ASES): Patient Self-Report Section

#### 1. Pain:

How bad is your pain today? (mark an “X” on the line)

---

No pain at all

Pain as bad  
as it can be

#### 2. Satisfaction:

Overall, what is your level of satisfaction with your shoulder?

---

Poor

Excellent

**3. Function:** Circle the number in the box that indicates your ability to do the following activities:

**0 = Unable to do; 1 = Very difficult to do; 2 = Somewhat difficult; 3 = Not difficult**

Activity	Right arm				Left arm			
1. Put on a coat	0	1	2	3	0	1	2	3
2. Sleep on your painful or affected side	0	1	2	3	0	1	2	3
3. Wash back/do up bra in back	0	1	2	3	0	1	2	3
4. Manage toileting	0	1	2	3	0	1	2	3
5. Comb hair	0	1	2	3	0	1	2	3
6. Reach a high shelf	0	1	2	3	0	1	2	3
7. Lift 10 lbs. above shoulder	0	1	2	3	0	1	2	3

8. Throw a ball overhand	0 1 2 3	0 1 2 3
9. Do usual work – List: _____	0 1 2 3	0 1 2 3
10. Do usual sport – List: _____	0 1 2 3	0 1 2 3

CONSTANT SCORE							
Dominance		Affected side		Normal side			
left	right	left	right	left	right		
Pain							
severe 0, moderate 1-5, mild 6-10, none 11-15		/ 15		/ 15			
Activities of Daily Living							
Work		/ 4		/ 4			
0 (unable) – 4 (full w/o restriction)							
Recreation/sport		/ 4		/ 4			
0 (unable) – 4 (full activities)							
Sleep		/ 2		/ 2			
0 (grossly disturbed) – 2 (undisturbed)							
Ability to work at the level: (check one)		 none	 none	 none	 none		
		 waist	 waist	 waist	 waist		
		 xiphoid	 xiphoid	 xiphoid	 xiphoid		
		 neck	 neck	 neck	 neck		
		 head	 head	 head	 head		
		 above head	 above head	 above head	 above head		
Motion (passive)							
Forward flexion / elevation		Degrees		Degrees			
Abduction		Degrees		Degrees			
ER		Degrees		Degrees			
IR		Level		Level			
Motion (active)							
Hand behind head (elbow forward)		Yes / No		Yes / No			
Hand behind head (elbow back)		Yes / No		Yes / No			
Hand on head (elbow forward)		Yes / No		Yes / No			
Hand on head (elbow back)		Yes / No		Yes / No			
Full elevation from top of head		Yes / No		Yes / No			
Active motion							
Dorsum of hand to: (check one)		 lateral thigh		 lateral thigh			
		 (0)		 (0)			
		 ER		 ER			
		 hand behind head with elbow held forward		 hand behind head with elbow held forward			
		 (2)		 (2)			
		 buttock		 buttock			
		 (2)		 (2)			
		 hand behind head with elbow held back		 hand behind head with elbow held back			
		 (2)		 (2)			
		 lumbosacral junction		 lumbosacral junction			
		 waist		 waist			
		 12 th dorsal vertebra		 12 th dorsal vertebra			
		 interscapular region (T7)		 interscapular region (T7)			
Power							

1. trial	Lb	Lb
2. trial	Lb	Lb
3. trial	Lb	Lb

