**SECONDARY:**

1) The American Shoulder and Elbow Surgeon's (ASES) score is a shoulder specific assessment tool developed by the American Shoulder and Elbow Society for use in all types of shoulder problems (Appendix A)(31). It consists of both patient self-assessment and physician assessment. The patient self-evaluation is divided into two sections: pain and activities of daily living (ADL). Pain is recorded on a visual analogue scale and ADL's are recorded on a numeric scale. The overall score is an equal weight of the two sections and produces a score out of 100. The higher the score, the better the outcome. The physician assessment is divided into four segments: range of motion, physical signs, strength and instability. The results of the physician assessment do not provide a score.

Europeans favor the Constant Score(30) (Appendix A). It has been validated, normalized in comparison to disease free patients and places greater emphasis on range of motion and strength. The European shoulder society has adopted the Constant Score for functional assessment of the shoulder. The Constant Score records a variety of shoulder measurements including an objective test of strength using a spring loaded measuring device. The Constant Score reflects an overall clinical functional assessment. This instrument is based on a 100-point scoring system calculated from a self-assessment portion that evaluates pain and ability to perform tasks of daily living, and a clinical assessment which tests active range of shoulder motion and strength. The higher the score the better the outcome.

2) Further secondary outcomes which will be monitored during the post-operative course include: operative times of the two procedures, complications, and the incidence of revision surgery in each procedure.

The MRI or Ultrasound will determine the healing rates of both procedures. It is imperative to determine the relative healing rates as cuff integrity following surgery correlates with function and strength.

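### The Constant score form records elevation and abduction in degrees only as passive motion, although Section 4.8 says the score tests active motion

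*Combined protocol and SAP*

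**What the plan says.** Section 4.8 (Secondary) names the Constant score as a secondary outcome and says of it: "This instrument is based on a 100-point scoring system". It describes the clinical component as "a clinical assessment which tests active range of shoulder motion and strength", and it says that the score "places greater emphasis on range of motion and strength". Section 4.9 has the blinded assessor carry out the physical part and refers to Appendix A for it. Section 4.10 compares the Constant score between the two groups at 8 years.

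The Constant form in Appendix A has three motion blocks:

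- The first is headed "Motion (passive". It has four rows: "Forward flexion / elevation", abduction and external rotation, each in degrees, and internal rotation by level. All are recorded for the affected and the normal side.
- The second is headed "Motion (active". It has five Yes/No rows, from "Hand behind head (elbow forward" to "Full elevation from top of head".
- The third is a further active block of check-boxes for hand positions, some with points printed beside them.

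**The concern.** The protocol's definition of the score and the form used to collect it point to different measurements. Passive range is how far the examiner can move the arm, while active range is how far the patient can. Passive range can be kept when the patient cannot raise the arm, so it may miss a loss of cuff function.

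That distinction matters for this comparison. Section 1 reports that double-row repair was associated with a greater healing rate in the original trial, and Section 4.8 links cuff integrity to function and strength. Active motion is therefore one of the places where a difference in healing could show in a clinical score.

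Timing adds weight. Section 4.6 allows one clinic visit and no follow-up afterwards, so active readings not taken at that visit cannot be recovered.

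**Working it through.** There is no power or sample-size figure to reproduce. The check compares the definition in Section 4.8 with the fields on the Appendix A form, movement by movement.

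| Movement | Passive field | Active field in degrees | Other active field |
|---|---|---|---|
| Forward elevation | 1, degrees | 0 | 1 Yes/No item, "Full elevation from top of head" |
| Abduction | 1, degrees | 0 | none |
| External rotation | 1, degrees | 0 | hand-to-head positions |
| Internal rotation | 1, level | 0 | check-one list of reaches up the back |

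For the two rotations, the matching of active items to movements is my reading of the form. An external-rotation label stands among the hand-behind-head check-boxes, and the reach list, like the passive internal-rotation row, records a level.

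1. All three degree fields are under the passive heading. The active blocks contain none.
2. The rotations appear to have an active counterpart in the hand-position items. Elevation has a single Yes/No item. Abduction has nothing, and the word does not occur elsewhere on the form.
3. No section says how the degree fields enter the score, or that active degrees are recorded on another page.
4. Two possibilities follow. If the degree fields are scored, the score uses passive motion, against Section 4.8. If they are not scored, the score has no active degree measure of elevation or abduction.

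**Can the affected points be counted?** The form prints maxima for pain (15), work (4), recreation or sport (4) and sleep (2), and 15 + 4 + 4 + 2 = 25. The other 100 − 25 = 75 points must be shared among working level, motion and power, and neither the form nor the text shows how. In the motion blocks, the only printed points are values of 0 and 2 beside some hand positions in the last block. The share resting on elevation and abduction therefore cannot be derived. The 75 points are what the form leaves unallocated and are not an estimate of that share.

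**Can the table be trusted?** The passive heading with its four rows and the first active heading with its five rows are in order, with matching entries for both sides. The clear disorder begins after them, in the hand-position block, where external-rotation items are mixed into the list of reaches. No legible item in that block mentions elevation or abduction, but a row lost there cannot be excluded.

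**The case against.** The strongest reply is that Section 4.8 asks for active motion without saying that it must be in degrees, or that elevation and abduction are scored items. The form does have two active blocks, and the only points printed in the motion part stand in one of them, with none beside a passive field. On that reading, the scored motion is already active and the passive degrees are descriptive. The need for active degrees would then come from the conventional scoring of the instrument, which the documents do not reproduce. The table is also damaged, so the missing fields may exist on the original form.

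Part of this stands. The documents do not show that passive degrees are scored, and the original form has to be checked before anything is changed. It does not remove the mismatch. Even if only the active blocks count, the form has no active item at all for abduction, and only a Yes/No answer for elevation, in a score that Section 4.8 says emphasises range of motion. The headings and rows that show this are the legible ones.

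A reader might also infer several stronger things that the documents do not support:

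- **Active elevation is missing altogether.** One Yes/No item touches it.
- **The score will give full credit to failed repairs and shrink the difference between arms.** This needs passive degrees to be scored, which no section states.
- **The result will not be comparable with the 2-year score.** The 2-year form and scoring are not in the documents. Section 1 says the same outcomes will be measured, and if the same form was used then, changing the scored fields without keeping the passive ones could itself harm comparability.
- **One arm is favoured.** Both arms use the same form, completed by a blinded assessor.

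**Conclusion.** The point holds as a mismatch between Section 4.8 and the Appendix A form as shown. Active abduction is not recorded, active elevation is recorded only as Yes/No, and their degree readings are passive. The score would either rest on passive degrees or lack an active degree measure of these two movements.

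The size in points is unknown, because there is no scoring key. The consequence is for the validity and sensitivity of one secondary outcome, equally in both arms. Section 4.10 bases treatment effectiveness on the primary variable alone, so the WORC comparison and the conclusion drawn from it are untouched.

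The verdict rests on two assumptions: that no active elevation or abduction field was lost from the disordered part of the table, and that such readings are not collected on a page outside the documents. It is still worth settling before the visits, since the single visit gives no second chance and the remedy is cheap.

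**What to change.** 1. Check the original Constant form. If it already has active elevation and active abduction in degrees, only step 3 is needed.
2. If not, add both fields in degrees, for the affected and the normal side, to be read by the same blinded assessor at the same visit.
3. State in Section 4.9 that the motion component of the Constant score is calculated from the active fields, and attach the scoring key.
4. Keep the passive fields. If the 2-year score was calculated from them, the 8-year score can then also be calculated that way, and the two versions reported side by side.

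The cost is one form revision, for which the trial management section already provides dated changes, and two extra readings per shoulder. That takes a minute or two of a visit for which Section 4.7 anticipates about 20 minutes with the assessor.
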